2.8.1.1 Adverse events of special interest / grouping of AEs

Not applicable.

Novartis	For business use only	Page 20 of 33
SAP		CSAF312B12201

2.8.1.2 Adverse event reporting for clinical trial safety disclosure

For the legal requirements of ClinicalTrials.gov, two required tables on TEAEs which are not serious adverse events with an incidence greater than 5% and on TEAEs and SAEs suspected to be related to study treatment will be provided by system organ class and preferred term on the safety set population.

If for the same subject, several consecutive AEs (irrespective of study treatment causality, seriousness and severity) occurred with the same SOC and PT:

- a single occurrence will be counted if there is ≤1 day gap between the end date of the preceding AE and the start date of the consecutive AE
- more than one occurrence will be counted if there is >1 day gap between the end date of the preceding AE and the start date of the consecutive AE

For occurrence, the presence of at least one SAE (respectively non-SAE) has to be checked in a block e.g., among AEs in a ≤ 1 day gap block, if at least one SAE is occurring, then one occurrence is calculated for that SAE.

The number of deaths resulting from SAEs suspected to be related to study treatment, and SAEs irrespective of study treatment relationship will be provided by SOC and PT.

2.8.2 Deaths

Deaths will be listed separately.

2.8.3 Laboratory data

Not applicable.

2.8.4 Other safety data

Where laterality applies, each eye will be summarized separately.

Corrected Visual Acuity

Snellen visual acuity (VA) testing in each eye will be conducted. The Snellen numerator and denominator will be entered in the eCRF. ETDRS will be derived from the Snellen visual acuity for summary (Table 2-5).

Table 2-5 Converting Snellen Fraction to Approximate ETDRS Letters Score

Snellen Fraction/ decimal	Approximate ETDRS Letters Score
≤ 0.005	0
> 0.005 to 0.015	1
> 0.015 to 0.020	3
> 0.020 to 0.025	5
> 0.025	85 + (50*log10[Snellen fraction]) rounded to the nearest integer

Novartis	For business use only	Page 21 of 33
SAP		CSAF312B12201

If numerator Snellen = 0 and denominator Snellen = 0, then ETDRS letters score is taken as missing.

Descriptive summaries (mean, median, 25th percentile, 75th percentile, standard deviation, minimum and maximum, the number of non-missing observations, and 95% confidence interval) of change from baseline VA values will be presented at each study visit by treatment group.

Intraocular Pressure

Intraocular pressure (IOP) measurements will be recorded in mmHg and rounded to the nearest whole number for summary.

Descriptive summaries (mean, median, 25th percentile, 75th percentile, standard deviation, minimum and maximum, the number of non-missing observations, and 95% confidence interval) of change from baseline IOP values will be presented at each study visit by treatment group.

Slit Lamp Exam and Fundus Exam/Ophthalmoscopy

Slit lamp and Fundus exams will be performed, and results will be captured in the source document at each visit. The eCRF will record only if those assessments were indeed performed or not for compliance perspective.

Subject listing will be provided.

Corneal Endothelial Cell Microscopy

At the Baseline and End of Treatment Visits, Specular microscopy of the corneal endothelial cell images will be obtained by the Investigator and submitted to the Central Reading Center (CRC) to determine the changes in endothelial cell count, density, and shape from the initial baseline to the end of treatment.

Listing of the parameters will be provided by subject by visit.

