Medical history / current medical conditions	X								
Previous /Con Meds	Х	Х	Х		Х	Х	Х	Х	Х
Inclusion / Exclusion criteria	Х		Х						
Pregnancy test (dipstick/strip)			S					S	
Adverse Events	Х	Х	Х		Х	Х	Х	Х	Х
Anesthetic test	Х								
Placebo response mitigation training video and knowledge check	S			S ¹					
Dispense electronic diary	S								
Pain Severity VAS	X ²	R	\mathbb{R}^3	R⁴	R^4	R^4	R ⁴		
Pain Frequency VAS	X ²	R		R ⁴	R^4	R ⁴	R ⁴		
Artificial tears use	X ²	R		R⁴	R ⁴	R ⁴	R ⁴		
Rescue medications	X ²	R		R ⁴	R ⁴	R^4	R ⁴		
OPAS Questionnaire	Х		X ⁶		X ⁶	X ⁶	X ⁶	X ⁶	
Pain Characterization Questionnaire	Х								

Period	Screening		Treatment				Post Treatment Follow-up		
Visit Name	Visit 1 Screening	Phone Check-in	Visit 2 Baseline	Visit 2 Randomization	Visit 3	Visit 4	Visit 5	Visit 6 / EOT	Follow-up Contact / EOS
Days	-84	-42 ± 7	1	1	14 ± 2	28 ± 2	56 ± 2	84 ± 2	EOT + 4
Visual Acuity	Χ		X					X	
Slit lamp examination	Х		X		Х	Х	Х	Х	
Signs evaluation: (Corneal fluorescein staining; Conjunctival lissamine staining. Conjunctival redness; Schirmer score)	X		х		Х	х	х	х	
Contact IRT	Х			Х	Х	Х	Х	Х	
Intraocular Pressure (IOP)			Х					Х	
Ophthalmoscopy dilated fundus exam			Х					Х	
Corneal endothelial cell microscopy			Х					Х	
In vivo confocal microscopy ⁷			X					X	
Dispense study medication				S ⁸	S	S	S		
Collect electronic diary								S	
Collect study medication					S	S	S	S	
Electronic diary compliance check ⁹			S		S	S	S	S	

^X Assessment to be recorded in the clinical database or received electronically from a vendor

S Assessment to be recorded in the source documentation only

Reminder for the tasks to be completed by the subject outside of the clinical site

¹ The Pain Assessment Knowledge Check can be optional for any subject who had completed the Knowledge Check already during Screening Visit (Visit 1).

² Two entries to be completed on the same day of screening. The first entry is to be made at the time of the on-site screening visit, the second entry and all subsequent entries are to be completed at home before their evening dose of study medication.

³ Confirm eligibility based on the eDiary data.

⁴ Remind the subject to complete the once daily eDiary recording prior to the evening dose of study medication every day until the evening prior to the EOT visit.

⁶ Enter the PIN code and select the scheduled visit on the Visit Selection menu to allow the study subject to complete the questionnaire on the tablet device

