8.4.7 Corneal Endothelial Cell Microscopy

Each site must use the specified brand of equipment for use on all subjects at the site. Certification of the equipment and examiners at each investigative site will occur prior to evaluation of study subjects. At the Baseline and End of Treatment Visits Specular microscopy of the corneal endothelial cell images will be obtained by the Investigator and submitted to the Central Reading Center (CRC) to determine the changes in endothelial cell count, density, and shape from the initial baseline to the end of treatment. A standardized procedure for the collection of the Specular microscopy images will be provided by the CRC in a separate manual.

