12.5.1 Safety endpoints

For all safety analyses, the safety set will be used. The safety assessments are adverse events (ocular and non-ocular), slit lamp biomicroscopy, IOP, visual acuity, ophthalmoscopy, and corneal endothelial cells evaluations. All listings and tables will be presented by treatment group.

Safety summaries (tables, figures) include only data from the on-treatment period with the exception of baseline data which will also be summarized where appropriate (e.g. change from baseline summaries). In addition, a separate summary for death including on treatment and post treatment deaths will be provided. In particular, summary tables for adverse events (AEs) will summarize only on-treatment events, with a start date during the on-treatment period (treatment-emergent AEs).

The on-treatment period starts from the date of the first administration of study treatment to 4 days after the date of the last administration of study treatment.

The safety analysis will consist of descriptive summaries. Continuous variables will be presented with n, mean, SD, median, minimum and maximum. Categorical data will be displayed with frequency and percentage.

Adverse events

All information obtained on adverse events will be displayed by treatment group and subject.

The number (and percentage) of subjects with treatment emergent adverse events (events started after the first dose of study medication or events present prior to start of double-blind treatment but increased in severity based on preferred term) will be summarized in the following ways:

- by treatment, primary system organ class and preferred term.
- by treatment, primary system organ class, preferred term and maximum severity.
- by treatment, Standardized MedDRA Query (SMQ) and preferred term.

Ocular and non-ocular adverse events will be summarized separately. Separate summaries will be provided for study treatment related adverse events, death, SAE, other significant adverse events leading to discontinuation.

Subject listings of all adverse events will be provided. Deaths and other serious or clinically significant non-fatal adverse events will be listed separately. A subject with multiple adverse events within a primary system organ class is only counted once towards the total of the primary system organ class.

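### The SAP only lists the centrally read corneal endothelial cell results by subject, although the protocol plans descriptive safety summaries by treatment group and the SAP declares no change

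*SAP*

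**What the plan says.** **Endothelial cells in the protocol.** Section 12.5.1 sets the scope: "The safety assessments are adverse events (ocular and non-ocular), slit lamp biomicroscopy, IOP, visual acuity, ophthalmoscopy, and corneal endothelial cells evaluations". It then sets the form: "The safety analysis will consist of descriptive summaries. Continuous variables will be presented with n, mean, SD, median, minimum and maximum". The same section uses the Safety Set, asks for output by treatment group, and exempts none of the named assessments. Section 8.4.7 sends the specular microscopy images to a central reading center "to determine the changes in endothelial cell count, density, and shape from the initial baseline to the end of treatment". Table 8-1 schedules the images at Baseline and at Visit 6/EOT. The protocol summary places this examination among the key safety assessments.

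**Endothelial cells in the SAP.** Section 2.8.4 restates that purpose and then specifies a single output: "Listing of the parameters will be provided by subject by visit". In the same section, visual acuity and IOP each get descriptive statistics of change from baseline by treatment group, including a 95% confidence interval. Section 4, reserved for changes to the protocol's analyses, is marked not applicable.

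**Slit lamp and fundus.** Protocol 8.4.4 and 8.4.6 place the results in source documents. SAP 2.8.4 agrees and adds: "The eCRF will record only if those assessments were indeed performed or not for compliance perspective". The planned output is a subject listing. Table 8-1 nevertheless marks both examinations X, which its legend explains as "Assessment to be recorded in the clinical database or received electronically from a vendor"; a separate code, S, is kept for source-only items. Protocol 8.4 routes any abnormality that the investigator considers clinically significant to the ocular medical history page or the AE page of the eCRF.

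**The concern.** The trial certifies equipment and examiners and pays for central reading in order to measure change in the endothelium, and then plans no output that describes that change by arm. A listing shows individual values. It gives no arm mean, no spread and no summary of change.

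The 12-week exposure is there partly to assess the safety of prolonged TRPV1 inhibition in the eye (Protocol 4.2). The earlier clinical ocular dosing described in that section lasted 7 days and 72 hours. The endothelial data are therefore among the new safety information that this trial can provide.

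Adverse event reporting does not fill the gap. It works one subject at a time and depends on the investigator's view that a finding is clinically significant. A modest shift in one arm may cross that line in nobody. The documents also do not say that central readings are returned to the investigator.

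**Working it through.** The point rests on comparing text. No figure in the plan needs reproducing.

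**Step 1. Planned form against planned output.** Protocol 12.5.1 names five safety assessments besides adverse events. SAP 2.8.4 treats them as follows:

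| Assessment | What is available for analysis | Output in SAP 2.8.4 |
|---|---|---|
| Visual acuity | Snellen values, converted to letters | By-arm summary of change, with 95% CI |
| IOP | mmHg | By-arm summary of change, with 95% CI |
| Endothelial cells | Central-reader count, density, shape | Listing only |
| Slit lamp | Performed / not performed | Listing only |
| Fundus | Performed / not performed | Listing only |

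Two are summarised and three are listed: 2 + 3 = 5. Endothelial microscopy is the only one of the three listed assessments whose results are available for a table.

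**Step 2. Does a general rule supply the missing table?** Two SAP lines might. Section 2.1 says that continuous variables get descriptive statistics by treatment group, and 2.8.4 opens by saying that each eye is summarised separately where laterality applies. However, the by-treatment-group rule in 2.1 yields where something else is specified, and the endothelial paragraph specifies a listing. The visual acuity and IOP paragraphs name their summaries outright. A programmer following 2.8.4 would produce the listing and nothing more.

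**Step 3. Is the difference declared?** SAP section 4 declares nothing.

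**Step 4. How large is the listing?** With about 150 subjects, two eyes and two scheduled visits, there are up to 150 × 2 × 2 = 600 eye-visit records. With both eyes on one row, this is 150 × 2 = 300 rows. Both are upper figures, since they assume that every subject has readable images in both eyes at both visits. At either size, a reader cannot judge arm-level change by eye.

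**Step 5. Slit lamp and fundus.** Protocol 8.4.4 and 8.4.6 and SAP 2.8.4 agree on source-only results, so the SAP does not depart from the protocol on data capture. The mismatch is with two other parts of the protocol: the X code in Table 8-1 and the descriptive summaries in 12.5.1. A performed/not performed flag cannot yield a summary of findings.

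**What is not calculated.** The documents give no SD for endothelial change, so the precision of an arm mean or difference cannot be stated from them.

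**The case against.** **12.5.1 is a general paragraph.** It does not specify an endothelial change table, and it mentions listings as well as tables. This is true. However, it names the assessment, says what the safety analysis consists of, and gives the statistics for continuous variables without exception. A listing alone does not meet that.

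**Clinically significant endothelial change is already reportable.** Protocol 8.4 covers every safety parameter, so a marked change in one subject can become an adverse event, and adverse events are summarised by arm. This stands, and it limits the gap to shifts that are not clinically significant in any individual. A reader might infer that endothelial harm would never appear as an adverse event because it is slow and silent. The documents say nothing about its course, and the point does not need that claim.

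**Slit lamp and fundus.** A reader might infer that these findings never reach the database, or that the SAP dropped them. Neither is supported. Clinically significant findings enter the eCRF as ocular history or adverse events, and source-only results are the protocol's own rule. One can also argue that a performed/not performed flag satisfies the X code. What stays out is the examination result itself and any finding judged not clinically significant.

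**Scope of the remedy.** A reader might also infer that a confidence interval for each difference from placebo is owed. Section 12.5.1 promises only descriptive statistics, and the interval that the SAP gives for visual acuity and IOP is listed among the by-group statistics. Nor does the protocol call for a new eCRF field for the examinations. SAP 5.4 already handles a site data problem, so collection was under way when the SAP was written and adding fields would not be trivial.

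**Conclusion.** The point holds for endothelial microscopy. The SAP delivers less than Protocol 12.5.1 describes for a key safety assessment and does not say so. The consequence is that no by-arm summary of change in count, density or shape is produced, and a between-arm shift below individual clinical significance would go undescribed.

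The conclusion rests on reading 12.5.1 as applying to every assessment it names, and on the specific listing instruction in 2.8.4 prevailing over the SAP's general text. It needs no assumption about effect size or variability, and it does not suggest that SAF312 affects the endothelium.

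For slit lamp and fundus, the point is smaller: an inconsistency of wording, mainly within the protocol, and a reporting route that the SAP should state. Neither part touches the primary efficacy analysis.

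**What to change.** 1. Add to SAP 2.8.4 one descriptive table on the Safety Set, by treatment group and by eye. It should give baseline, EOT and change from baseline for endothelial cell density, count and shape, with n, mean, SD, median, minimum and maximum. A 95% confidence interval for change, as already given for visual acuity and IOP, is optional. Keep the listing.
2. State in the table specification which image counts as EOT for a subject who stops early, because SAP 2.1.1.5 allocates assessments to visits by study day.
3. In SAP section 4, state that slit lamp and fundus examinations are reported through adverse events and listings only. Reconcile this with Protocol 8.4.4, 8.4.6, 12.5.1 and the X code in Table 8-1.

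The cost is one table programmed from central-reader data already planned, and a few sentences of text. No trial procedure, eCRF page or data collection changes. If the sponsor prefers to keep the listing alone for endothelial data, the minimum is to declare that in section 4 with a reason, although the by-arm information would then still be missing.

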2.9 Pharmacokinetic endpoints

Not applicable.

2.10 PD and PK/PD analyses

Not applicable.

2.11 Patient-reported outcomes

In addition to the VAS, patient-reported outcomes include the following:

• OPAS questionnaire subscales

No test will be performed on the PRO endpoints that are not pertaining to the primary endpoint. Please refer to Section 2.7 and Section 2.13 for detail.

Novartis	For business use only	Page 22 of 33
SAP		CSAF312B12201

2.12 Biomarkers

Not applicable.

2.13 Other Exploratory analyses

Exploratory endpoints include:

- Frequency of artificial tears/gel/lubricant use over the 12-week treatment period
- Frequency of rescue medication use over the 12-week treatment period
- Change from Baseline to Week 12 in total corneal nerve fiber length
- Presence of microneuromas
- Density of corneal dendritiform cells

The analysis will be based on FAS. Descriptive summaries (mean, median, 25th percentile, 75th percentile, standard deviation, minimum and maximum, the number of non-missing observations, and 95% confidence interval) of frequency of artificial tears/gel/lubricant use and frequency of rescue medication use will be presented by week and treatment group.

The details of the rest exploratory analysis will be documented in Data Exploration Strategy separately. If any of the exploratory analysis is considered of clinical or regulatory relevance, it will be included in an SAP/CSR via amendment or addendum process as appropriate.

2.14 Interim analysis

Not applicable.

3 Sample size calculation

Assuming a true treatment difference in change from baseline in weekly mean pain severity VAS of 15 mm and a SD of 23 mm, a sample size of 50 subjects per arm provides approximately 83% power that the primary analysis will be statistically significant at the two-sided 5% significance level adjusted by 2 comparisons.

See Table 3-1 for power to detect a significant difference from placebo under various assumed treatment-effect of weekly mean pain severity VAS and SD.

Query Advisor 7.0 is used for the estimate.

Novartis	For business use only	Page 23 of 33
SAP		CSAF312B12201

Table 3-1Power to detect a significant difference from placebo under different
assumed treatment effects and SD with N = 50 pts/arm

	Treatment effect: difference from placebo in change from baseline in weekly mean pain severity VAS	
SD of change from baseline in weekly mean I pain severity VAS	15	20
17	98%	>99%
20	92%	>99%
23	83%	97%

The sample size may increase by up to 20% (i.e. 60 pts/arm) in order to maintain power in case dropout increases during the pandemic.

4 Change to protocol specified analyses

Not applicable.

5 Appendix

5.1 Imputation rules

5.1.1 AE date imputation

5.1.1.1 Adverse event end date imputation

1. If the AE end date month is missing, the imputed end date should be set to the earliest of the (treatment follow-up period date, 31DECYYYY, and/or date of death).

2. If the AE end date day is missing, the imputed end date should be set to the earliest of the (treatment follow-up period date, last day of the month, and/or date of death).

3. If AE year is missing or AE is ongoing, the end date will not be imputed.

5.1.1.2 Adverse event start date imputation

The following table explains the notation used in the logic matrix. Please note that **missing start dates** will not be imputed.

	Day	Month	Year
Partial Adverse Event Start Date	Not used	MON	YYYY
Treatment Start Date	Not used	TRTM	TRTY

The following matrix explains the logic behind the imputation.

Novartis SAP		For business use only			Page 24 of 33 CSAF312B12201
		MON MISSING	MON < TRTM	MON = TRTM	MON > TRTM
	YYYY MISSING	(1) No convention	(1) No convention	(1) No convention	(1) No convention
	YYYY < TRTY	(2.a) Before Treatment Start	(2.b) Before Treatment Start	(2.b) Before Treatment Start	(2.b) Before Treatment Start
	YYYY = TRTY	(4.a) Uncertain	(4.b) Before Treatment Start	(4.c) Uncertain	(4.c) After Treatment Start
	YYYY > TRTY	(3.a) After Treatment Start	(3.b) After Treatment Start	(3.b) After Treatment Start	(3.b) After Treatment Start

Before imputing AE start date, find the AE start reference date.

- 1. If the (imputed) AE end date is complete and the (imputed) AE end date < treatment start date then AE start reference date = min (informed consent date, earliest visit date).
- 2. Else AE start reference date = treatment start date

Impute AE start date

- 1. If the AE start date year value is missing, the date uncertainty is too high to impute a rational date. Therefore, if the AE year value is missing, the imputed AE start date is set to NULL.
- 2. If the AE start date year value is less than the treatment start date year value, the AE started before treatment. Therefore:
 - a. If AE month is missing, the imputed AE start date is set to the mid-year point (01JulYYYY).
 - b. Else if AE month is not missing, the imputed AE start date is set to the mid-month point (15MONYYYY).
- 3. If the AE start date year value is greater than the treatment start date year value, the AE started after treatment. Therefore:
 - a. If the AE month is missing, the imputed AE start date is set to the year start point (01JanYYYY).
 - b. Else if the AE month is not missing, the imputed AE start date is set to the later of (month start point (01MONYYYY), AE start reference date + 1 day).
- 4. If the AE start date year value is equal to the treatment start date year value:
 - a. And the AE month is missing the imputed AE start date is set to the AE reference start date + 1 day.
 - b. Else if the AE month is less than the treatment start month, the imputed AE start date is set to the mid-month point (15MONYYYY).

Novartis	For business use only	Page 25 of 33
SAP		CSAF312B12201

c. Else if the AE month is equal to the treatment start date month or greater than the treatment start date month, the imputed AE start date is set to the later of (month start point (01MONYYYY), AE start reference date + 1 day).

If complete (imputed) AE end date is available and the imputed AE start date is greater than the (imputed) AE end date, then imputed AE start date should be set to the (imputed) AE end date.

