Conditions that were already present at the time of informed consent should be recorded in medical history of the subject.

Adverse events (including lab abnormalities that constitute AEs) should be described using a diagnosis whenever possible, rather than individual underlying signs and symptoms.

Adverse event monitoring should be continued until the end of study visit.

Once an AE is detected, it should be followed until its resolution or until it is judged to be permanent (e.g. continuing at the end of the study), and assessment must be made at each visit (or more frequently, if necessary) of any changes in severity, the suspected relationship to the interventions required to treat it, and the outcome.

Information about adverse drug reactions for the investigational drug can be found in the Investigator's Brochure (IB).

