1.1 Study design

Figure 1-1 Study Design

This study is a Phase 2 randomized, double-blinded, multi-center, parallel group, placebocontrolled evaluation of the safety and efficacy of SAF312, 5 mg/ml and 15 mg/ml eye drops versus placebo used twice-daily in both eyes for 12 weeks. Eligible subjects will have undergone refractive surgery (i.e., PRK, LASIK, LASEK, RK, or SMILE) or cataract surgery in both eyes, with or without refractive enhancement in one or both eyes at least 4 months prior to Screening, and have been suffering from chronic ocular pain as a result of the surgery. Both eyes do not necessarily need to have undergone surgery on the same day. If the second eye underwent surgery on a different day than the first eligibility for time since surgery would be based on the date of the second surgery. In cases where more than one procedure was performed on an eye (e.g. refractive surgery with CICP followed some time later by cataract surgery, or cataract surgery followed some time later by refractive enhancement), the Screening visit must be ≥ 4 months after the most recent procedure. Eligible patients must also demonstrate chronicity of the pain as described in the inclusion criteria.

The study will consist of a 12-week observation period starting from Screening Visit (Visit 1) until the Baseline/Randomization Visit (Visit 2). Subjects who qualify for randomization will then be asked to attend visits every 2 weeks for the first 4 weeks, and then monthly for the

Novartis	For business use only	Page 8 of 33
SAP		CSAF312B12201

remainder of the 12-Week treatment period. End of Treatment (EOT) will occur at Visit 6 when the subject receives the last study treatment. End of Study (EOS) will occur 4 days after EOT. Visit 6/EOT is the time point for primary analysis.

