2.8.1 Adverse events (AEs)

Summary tables for AEs will summarize for pre-treatment AEs and treatment emergent AEs (TEAEs) separately:

- Pre-treatment AEs are adverse events started between ICF signature and prior to the first administration of study treatment.
- TEAEs are adverse events started after the first administration of study treatment or events present prior to start of the treatment but increased in severity based on preferred term.

The number and percentage of subjects with AEs will be summarized for ocular and non-ocular respectively, by treatment, in the following ways:

- Primary system organ class and preferred term.
- Primary system organ class, preferred term and maximum severity.
- Standardized MedDRA Query (SMQ) and preferred term.

Separate summaries for TEAEs will be provided for study medication related AEs, death, serious adverse events (SAE), other significant AEs leading to discontinuation.

A subject with multiple adverse events within a primary system organ class is only counted once towards the total of the primary system organ class. All of these analyses will be based on the most updated MedDRA version available prior to the database lock.

All adverse events reporting will be included in the subject listings respectively.

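### Partial AE start dates before treatment are imputed to 1 July or mid-month with no floor at informed consent, so some recorded AEs get start dates before consent

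*SAP*

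**What the plan says.** SAP 5.1.1.2 has three rules for partial AE start dates that fall before treatment:

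- Rule 2.a, year before the treatment year and month missing: "If AE month is missing, the imputed AE start date is set to the mid-year point", 1 July of the recorded year.
- Rule 2.b, same situation but month known: "Else if AE month is not missing, the imputed AE start date is set to the mid-month point", the 15th.
- Rule 4.b, year equal to the treatment year: "Else if the AE month is less than the treatment start month, the imputed AE start date is set to the mid-month point", again the 15th.

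None of these compares its result with the consent date. The same section does define a reference date. If the AE ended before treatment, "AE start reference date = min (informed consent date, earliest visit date"; otherwise the reference is the treatment start date. That reference enters only rules 3.b, 4.a and 4.c. The section closes with a correction for an imputed start later than the end date: "then imputed AE start date should be set to the (imputed) AE end date".

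SAP 2.8.1 summarises AEs in two groups. The first is defined as follows: "Pre-treatment AEs are adverse events started between ICF signature and prior to the first administration of study treatment". The second, treatment-emergent AEs, takes events that start after first dose, or were present earlier and increased in severity. Protocol 10.1.1 counts AEs only from consent, and adds: "Conditions that were already present at the time of informed consent should be recorded in medical history of the subject".

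**The concern.** A recorded AE cannot have started before consent; anything earlier belongs in medical history. A rule that can place an AE start before consent therefore contradicts the protocol's definition. The contrast with concomitant medication (SAP 5.1.2.2) is useful. The same mid-year and mid-month conventions do no harm there, because a medication may well have been started before the study.

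What is at stake is the pre-treatment AE summary. Its definition in SAP 2.8.1 has a lower limit at consent as well as an upper limit at first dose. An event imputed to before consent fails the lower limit. It also fails the first limb of the treatment-emergent definition, and rightly so, because it did start before treatment. If it never worsened, no AE summary takes it in. The closing step of SAP 5.1.1.2 offers no rescue, because it only moves start dates earlier.

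**Working it through.** The documents give no figure on this point, so there is nothing to reproduce. The check applies the rules to the calendar.

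**Inputs**

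- Run-in: 84 days. SAP 1.1: "The study will consist of a 12-week observation period starting from Screening Visit (Visit 1". Protocol Table 8-1 puts consent and Visit 1 at Day -84, and SAP 2.1.1.2 counts that as 84 days before first dose.
- True AE start: from consent to the day before first dose (Protocol 10.1.1).
- Imputation rules 2.a, 2.b and 4.b as stated.

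**When rule 2.a can apply.** The AE year must precede the treatment year. The AE starts on or after consent, so consent is also in the earlier year.

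- Earliest consent: 1 January − 84 days = 9 October.
- Latest consent: 31 December, giving a first dose on 31 December + 84 days = 25 March (24 March in a leap year).
- Share of possible first-dose dates over four calendar years: 84 × 4 / 1,461 = 23%.

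**Distance from 1 July to consent**

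- To 9 October: 31 + 31 + 30 + 8 = 100 days.
- To 31 December: 31 + 31 + 30 + 31 + 30 + 30 = 183 days.

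The imputed date is thus 100 to 183 days before consent in every case. Example: first dose 1 February, consent 9 November. An AE recorded with only the earlier year gets 1 July, which is 131 days before consent.

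**Enumeration.** Taking every first-dose date in four years and every possible AE start day, rule 2.a covers 4 × (84 × 85 / 2) = 14,280 combinations. The imputed date precedes consent in 14,280 of 14,280.

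**Sensitivity to run-in length.** Neither document gives an upper window for the run-in, so it was varied from 77 to 200 days. The share is 100% at every length tested up to 183 days. It first drops at 184 days (67,344 / 68,080 = 98.9%), because 1 July to 1 January is 184 days. At 200 days it is 83.8%. The planned schedule leaves a margin of 100 days.

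**Mid-month rules.** The 15th precedes consent only if the event is in the consent month and consent was after the 15th. With AE onset uniform over the 84 days:

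| Rule | Dated before consent |
|---|---|
| 2.b | 11.0% |
| 4.b | 5.2% |
| Both | 6.0% |

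A hand check with 30-day months agrees. Consent on days 16 to 30 leaves 15 + 14 + … + 1 = 120 affected AE days. Averaged over 30 consent days, that is 4 per subject. Run-in days before the treatment month average 84 − 14.5 = 69.5, and 4 / 69.5 = 5.8%.

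**With a floor at consent.** Each affected start becomes the consent date, which lies before first dose. The share of rule 2.a dates before consent falls from 100% to 0%. All floored events meet the pre-treatment definition, taking the day of consent as included, and none becomes treatment-emergent.

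**The case against.** The strongest objection is to the consequence. SAP 2.8.1 does not say that the imputed date decides which summary an event enters. Where the SAP intends that, it says so: section 2.4.2 classifies medications by recorded or imputed dates. The matrix in 5.1.1.2 labels these cells as before treatment start, which is the correct side of first dose. A programmer who tests only against first dose would keep the event in the pre-treatment table. This stands. The loss follows from a literal reading and is not certain. The impossible date remains either way.

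A reader might also infer more than the documents support:

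- *That every such event leaves both summaries.* It does not. An event that later increases in severity enters the treatment-emergent table through the second limb of the definition.
- *That the safety comparison between arms is affected.* It is not. These events truly began before treatment, and Protocol 12.5.1 confines its AE tables to on-treatment events. The pre-treatment table is an addition in the SAP, and neither document calls it a safety reference for the observation period. All AEs stay in the listings.
- *That many events are lost.* Nothing shows this. Rule 2.a needs a missing start month and a run-in that crosses New Year. AEs are sought at Visit 1, the mid-run-in call and Visit 2; missing values are queried (Protocol 11.2); and the tables cover only treated subjects.

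**Conclusion.** The defect is real and minor. Rules 2.a, 2.b and 4.b lack a lower bound at consent. Rule 2.a cannot give a valid AE date on the planned schedule; this holds for any run-in up to 183 days and assumes consent at Visit 1. The figure of about 6% for the mid-month rules rests on assumed uniform onset over the run-in.

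Read literally with SAP 2.8.1, an affected event that does not worsen can be missing from the pre-treatment AE summary. No efficacy result, treatment-emergent comparison or listing loses an event. The documents do not give the number of partial dates; it is probably small. The change is worth making because the stated rule is wrong and cheap to correct, not because a conclusion of the trial depends on it.

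**What to change.** Amend SAP 5.1.1.2 as follows:

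- Rule 2.a: use the later of 01JulYYYY and the informed consent date when the AE year is the consent year.
- Rules 2.b and 4.b: use the later of 15MONYYYY and the informed consent date, only when the recorded month and year are those of consent.
- Query any recorded month before consent. Flooring it would overwrite a known month and could turn misfiled medical history into an AE.

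Use the informed consent date itself. Rules 3.b and 4.c also take a later-of form, but their bound is the reference date plus one day, and the reference is treatment start unless the AE ended before treatment. Copied into these rules, that bound would date an AE still ongoing at first dose to the day after treatment start and make it falsely treatment-emergent.

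The cost is one SAP phrase per rule, minor programming, and an occasional data query.
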